12. Post-organ and/or stem cell transplant whether or not with chronic immunosuppressive therapy.
13. Major surgery (per the investigator's judgment) within the 4 weeks prior to study entry or planned major surgery through the course of the study.
14. History of myocarditis, pericarditis, cardiomyopathy, transient ischemic attack or stroke, myocardial infarction, angina, coronary artery disease, congestive heart failure, clinically significant arrhythmia (including any arrhythmia requiring medication, treatment, or clinical follow-up).
15. Electrocardiogram (ECG) with clinically significant findings, or features that would interfere with the assessment of myocarditis/pericarditis, including any of the following:
 - Conduction disturbance (complete left or complete right bundle branch block or nonspecific intraventricular conduction disturbance with QRS \geq 120 ms, PR interval \geq 210 ms, any second- or third-degree atrioventricular block, or prolongation of the QT interval corrected according to Fridericia's formula [QTcF] [$>$ 450 ms])
 - Significant repolarization (ST-segment or T-wave) abnormality.
 - Significant atrial or ventricular arrhythmia; frequent atrial or ventricular ectopy (eg, frequent premature atrial contractions, 2 premature ventricular contractions in a row).
 - ST-elevation consistent with ischemia or evidence of past or evolving myocardial infarction.
16. History of diabetes mellitus type 1 or type 2, including cases controlled with diet alone.
Note: history of isolated gestational diabetes is not an exclusion criterion.
17. Thyroidectomy, or thyroid disease requiring medication during the last 12 months.

18. Uncontrolled hypertension, defined as systolic blood pressure ≥ 140 mmHg at enrollment or diastolic blood pressure ≥ 90 mmHg at enrollment.
Note: In case of diastolic values greater than 90 mmHg or systolic values greater than 140 mmHg, the measurement can be repeated after 30 minutes rest and the subject can be enrolled in case of 2 consecutive measurements fulfilling the inclusion criterion.
19. Major psychiatric illness and/or substance abuse problems during the past 12 months that in the opinion of the investigator would preclude participation.
20. Receipt of live attenuated vaccines from 30 days before Day 1 or receipt of any other vaccine in the period from 15 days before Day 1.
21. Use of experimental therapeutic agents within 3 months from the start of screening.

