11.5. Safety Analyses

No formal statistical testing of safety data is planned. Safety data will be analyzed descriptively (including 95% confidence intervals [CIs], if applicable).

Baseline for all safety parameters will be defined as the last value before the prime vaccination.

Adverse Events (Including Reactogenicity)

The verbatim terms used in the CRF by investigators to report adverse events will be coded using the Medical Dictionary for Regulatory Activities (MedDRA). All reported adverse events (solicited local, solicited systemic, and unsolicited) during the treatment period (ie, treatment-emergent adverse events, and adverse events that have worsened since baseline) will be included in the analysis. For each adverse event, the number and percentage of subjects who experience at least one occurrence of the given event will be summarized. Summaries, listings, datasets and/or subject narratives may be provided as appropriate, for those subjects who die, discontinue study vaccinations due to an adverse event, or experience a severe or serious adverse event. The analysis for solicited adverse events will be done on those subjects in the FA set for whom

reactogenicity assessments are available in the database. The analysis of unsolicited adverse events will be done based on the FA set.

Clinical Laboratory Tests

Laboratory data will be summarized by the type of laboratory test. Descriptive statistics (actual values and changes from reference) will be calculated for each laboratory analyte at baseline and at each scheduled time point. Graphical presentation of changes in laboratory tests will be made, as applicable. If the baseline value is not available, the value at screening will be used as baseline value. Laboratory abnormalities will be determined according to the toxicity grading tables included in [Attachment 1](#), and in accordance with the normal ranges of the clinical laboratory. Laboratory abnormalities will be tabulated per treatment group and scheduled time point.

Vital Signs and Electrocardiograms

Descriptive statistics of heart rate, blood pressure (systolic and diastolic), oral body temperature and ECG parameters (QTcF and PR interval) values and changes from baseline will be summarized at each scheduled time point. The percentage of subjects with values beyond pre-specified limits will be summarized.

Physical Examination

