12.1.3. Severity Criteria

Adverse events and laboratory data will be coded for severity using the toxicity grading tables in [Attachment 1](#). For adverse events not identified in the table, the following guidelines will apply:

Mild	Grade 1	Symptoms causing no or minimal interference with usual social and functional activities
Moderate	Grade 2	Symptoms causing greater than minimal interference with usual social and functional activities
Severe	Grade 3	Symptoms causing inability to perform usual social and functional activities

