Attachment 1: DMID Toxicity Table for Use in Trials Enrolling Healthy Adults (2014)

The abbreviations used in the following tables are:

ALT: alanine aminotransferase; aPTT: activated partial thromboplastin time; AST: aspartate aminotransferase; AV block: atrioventricular block; bpm: beats per minute; BUN: blood urea nitrogen; CK: creatine kinase; CPK: creatine phosphokinase; FEV₁: forced expiratory volume in 1 second; g: gram; HI: high; HPF: high power field; IU: international unit; IV: intravenous; K/CUMM: $\times 10^3/\text{mm}^3$; LLN: lower limit of normal; LO: low; mEq: milliequivalent; mm Hg: millimeter of mercury; ms: millisecond; N: normal; PT: prothrombin time; PTT: partial thromboplastin time; QTc: QT-interval corrected for heart rate; QTcB: Bazett's corrected QT interval; QTcF: Fridericia's corrected QT interval; RBC: red blood cell; Rx: therapy; s: second; U: unit; ULN: upper limit of normal

CLINICAL ADVERSE EVENTS

Cardiovascular	Mild (Grade 1)	Moderate (Grade 2)	Severe (Grade 3)
Arrhythmia		Asymptomatic, transient signs, no Rx required	Recurrent/persistent; symptomatic Rx required
Hemorrhage, blood loss	Estimated blood loss ≤ 100 mL	Estimated blood loss >100 mL, no transfusion required	Transfusion required
QTcF (Fridericia's correction) ^a or QTcB (Bazett's correction)	Asymptomatic, QTc interval 450-479 ms, OR Increase in interval <30 ms above baseline	Asymptomatic, QTc interval 480-499 ms, OR Increase in interval 30-50 ms above baseline	Asymptomatic, QTc interval ≥ 500 ms, OR Increase in interval ≥ 60 ms above baseline
PR interval (prolonged)	PR interval 0.21-0.25 s	PR interval >0.25 s	Type II 2nd degree AV block OR Ventricular pause >3.0 s
Respiratory	Mild (Grade 1)	Moderate (Grade 2)	Severe (Grade 3)
Cough	Transient-no treatment	Persistent cough	Interferes with daily activities
Bronchospasm, acute	Transient; no treatment; FEV ₁ 71%-80% of peak flow	Requires treatment; normalizes with bronchodilator; FEV ₁ 60%-70% (of peak flow)	No normalization with bronchodilator; FEV ₁ $<60\%$ of peak flow
Dyspnea	Does not interfere with usual and social activities	Interferes with usual and social activities, no treatment	Prevents daily and usual social activity or requires treatment

^a Inclusion dependent upon protocol requirements.

Gastrointestinal	Mild (Grade 1)	Moderate (Grade 2)	Severe (Grade 3)
Nausea	No interference with activity	Some interference with activity	Prevents daily activities

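### Three rows of the Attachment 1 toxicity table (low potassium, QTc change, total protein) misgrade if applied as printed and should be reconciled before grading

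*Protocol*

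**What the plan says.** Two sections make Attachment 1 the grading scale. Section 11.5 (Clinical Laboratory Tests) says "Laboratory abnormalities will be determined according to the toxicity grading tables included in" Attachment 1, together with the laboratory's normal ranges, and plans a tabulation by group and time point. Section 12.1.3 says "Adverse events and laboratory data will be coded for severity using the toxicity grading tables in" the same attachment; its general mild/moderate/severe definitions apply only to events that the table does not cover.

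- **QTc (cardiovascular block).** Each grade is met by an absolute value or by a rise. Grade 1 is "QTc interval 450-479 ms" or "Increase in interval <30 ms above baseline". Grade 2 is "QTc interval 480-499 ms" or "Increase in interval 30-50 ms above baseline". Grade 3 is 500 ms or more, or a rise of at least "60 ms above baseline".
- **Potassium, low row.** Grade 1 is printed as running from above the upper limit of normal (ULN) to 3.1, Grade 2 from below 3.1 to 3.0, and Grade 3 as below 3.0. The low rows for sodium and calcium are bounded by the lower limit of normal (LLN).
- **Total protein, low row.** Grade 1 is 5.2 to below LLN, Grade 2 is 5.0-5.4, and Grade 3 is below 5.0.

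**The concern.** A severity scale should give each abnormal value exactly one grade, and a worse value should never get a lower grade. None of the three rows meets this as printed. Safety is the primary objective, and the graded counts are part of how it is described.

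The potassium row feeds a planned table directly. Potassium carries no screening-only asterisk in Section 9.3.2, so it is measured after vaccination as well. The QTc gap lies between Grades 2 and 3. Section 11.8 uses related Grade 3 unsolicited events to pause vaccination and to withhold a subject's boost, so an unassigned range at that border is an unassigned range in the input to those rules. The total-protein overlap touches eligibility only: Exclusion Criterion 10 accepts Grade 1 and treats Grade 2 or 3 as out of range.

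**Working it through.** There is no stated figure to reproduce. The check applies the printed cells literally, with QTc in whole milliseconds and the highest grade met by either the absolute value or the rise.

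**QTc.** Inputs are the bands above and Section 4.2, which excludes subjects with "prolongation of the QT interval corrected according to Fridericia's formula" above 450 ms, so the screening baseline is at most 450 ms. For a rise r between 51 and 59 ms no change band applies, and the grade depends on baseline + r alone:

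- below 450 ms: no grade;
- 450-479 ms: Grade 1;
- 480-499 ms: Grade 2;
- 500 ms or more: Grade 3.

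A rise of 45 ms is always at least Grade 2 through the change band. Hence:

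| Baseline (ms) | Rise of 45 | Rise of 55 |
|---|---|---|
| 390 | 435, Grade 2 | 445, no grade |
| 400 | 445, Grade 2 | 455, Grade 1 |
| 424 | 469, Grade 2 | 479, Grade 1 |
| 425 | 470, Grade 2 | 480, Grade 2 |
| 450 | 495, Grade 2 | 505, Grade 3 |

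The 55 ms rise is ungraded up to a baseline of 394 ms (394 + 55 = 449). It is Grade 1 from 395 to 424 ms (424 + 55 = 479). The inversion ends at 425 ms. For other rises in the gap, the last inverted baseline is 479 - r, which is 428 ms for r = 51 and 420 ms for r = 59.

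*How often.* The schedule gives two post-vaccination ECGs per subject: (72 + 15) x 2 = 174. The protocol gives no SD for the change in QTc on a single ECG, so 10-15 ms is assumed, with no vaccine effect. P(50 < change < 60) is then about 3e-7 at SD 10 and 0.0004 at SD 15. The expected number in the whole trial is at most 174 x 0.0004 = 0.07.

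**Potassium.** There are two literal readings of the low Grade 1 cell:

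- *Above ULN and also no higher than 3.1:* no value qualifies. The band is empty, and a value from 3.1 up to LLN gets no low grade.
- *The span from ULN down to 3.1:* a value of 4.0 is Grade 1 low, as is every normal value.

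If the row were bounded by LLN (assumed 3.4-3.6 mmol/L, with ULN assumed 5.0-5.3, because the protocol gives neither), values of 3.6-5.0 would be ungraded and 3.3 would be Grade 1. Grades 2 and 3 are the same on every reading.

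*How many results.* The Time and Events Schedule has five chemistry samples after the prime in every group: three and seven days after the prime, the boost day before dosing, and three and seven days after the boost. That is 87 x 5 = 435 planned results.

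**Total protein.** A value of 5.3 g/dL meets both Grade 1 (if LLN exceeds 5.3) and Grade 2. The overlap runs from 5.2 to 5.4, or to just below LLN if LLN is 5.4 or lower. Section 9.3.2 marks total protein as measured only at screening.

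**The case against.** The strongest reply is that little of this reaches an analysis.

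Section 11.5 summarises QTcF by descriptive statistics, changes from baseline and the percentage beyond pre-specified limits, and does not invoke Attachment 1 there. Under Section 9.3.2 an ECG finding goes on the adverse event page only if it is clinically relevant. The QTc row also carries a footnote making its use depend on the protocol. A 51-59 ms rise would be very rare, and it would still show in the descriptive changes.

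The potassium cell looks like a slip. The fibrinogen low row has the same layout with LLN in that place, and Section 11.5 also refers to the laboratory's normal ranges, so a programmer may well use LLN. The cell could even be an error in reading the PDF. Finally, the table is presented as an external standard, so its QTc bands may be as published.

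Most of this stands, and it limits the point. It does not remove it. The protocol nowhere opts out of the QTc row: it schedules ECGs after each vaccination, and Section 12.1.1 makes clinically significant ECG changes an event of special interest. The fallback definitions in Section 12.1.3 do not apply to a finding that the table names. An external origin does not make a gap usable, and the sponsor has already added a troponin footnote to this copy.

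Three stronger readings are tempting, and the documents do not support them:

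- *That the planned QTc summaries would be wrong.* They do not use these grades.
- *That small random rises would fill Grade 1, because "Increase in interval <30 ms above baseline" has no lower bound.* The clause is indeed open, but a trivial rise on a normal ECG is not recorded as an adverse event and so is not graded. Whether to bound or remove the clause is a clinical choice outside this review.
- *That the laboratory pausing rule is compromised.* It uses Grade 3, and Grade 3 low potassium is intact.

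**Conclusion.** The point holds within limits. Applied as printed, Attachment 1 misgrades in three places.

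- **Low potassium.** This has the widest reach. The planned Grade 1 low counts, across up to 435 post-prime results, would either include every normal value or miss true mild lows. Which occurs depends on the reading chosen, and neither occurs if LLN is silently substituted. Grades 2 and 3 and the pausing rules are unaffected.
- **QTc change.** The scale is not monotone for 51-59 ms rises; for a 55 ms rise the inversion covers all baselines up to 424 ms. It matters only for an ECG finding recorded as an adverse event. With no vaccine effect and an assumed SD of up to 15 ms, at most about 0.07 such ECGs are expected, so the reason to correct it is its position at the Grade 2/3 border, not its frequency.
- **Total protein.** The overlap is real but confined to screening.

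No primary safety conclusion is shown to change. The correction is nevertheless worth making, because the protocol relies on this scale and the repair is cheap. All of this assumes that the cells read as extracted; the potassium cell in particular should be checked on the original page.

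**What to change.** Before grading, check the three rows on the original page and reconcile them with the source toxicity table and with the attachment's own use of LLN and ULN. After reconciliation:

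- the low-potassium Grade 1 band is bounded by the lower limit, as in the sodium and calcium low rows;
- every QTc rise has a stated grade, and a larger rise never grades below a smaller one from the same baseline;
- the total-protein Grade 1 and Grade 2 bands do not overlap.

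Which grade a 51-59 ms rise takes, and where the total-protein boundary falls, are for the sponsor to settle against the source; no threshold is proposed here. The cost is a corrected attachment and matching grading programs. No new data are needed.
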